7.3. Body Weight and Vital Signs

Body weight and vital signs will not be summarized or listed.

7.4. Prior and Concomitant Medications

Prior and concomitant medications will not be summarized or listed.

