- Pruritus assessments: Pruritus VAS and 5D-Itch at Baseline/Day 1 and at all subsequent in-clinic study visits

- For subjects with history of IBD (as appropriate, see Section 6.8.6):
 - IBD symptom severity assessment at Weeks 4, 8, and 12
 - Any evidence of active IBD seen on routinely performed colonoscopy will be captured at all in-clinic visits
- Symptom-directed PE, assessments for ascites and HE, vital signs, and body weight at Baseline/Day 1 and at all subsequent in-clinic study visits
- CP and MELD score calculations at Baseline/Day 1 and at all subsequent in-clinic study visits
- Blood chemistry, eGFR, hematology, and coagulation panel at Baseline/Day 1 and at all subsequent in-clinic study visits
- Lipid profile at Baseline/Day 1 and Weeks 4, 8, and 12
- C-Peptide, Insulin, and hemoglobin A_{1c} (HbA_{1c}) at Baseline/Day 1 and Week 12
- Urine pregnancy testing (females of childbearing potential only) at Baseline/Day 1 and Weeks 4, 8, 12
- Biomarker Testing at Baseline/Day 1 and Weeks 1, 4, 8, and 12 including but not limited to the following biomarkers:

cc1 [REDACTED]
[REDACTED]
[REDACTED]
[REDACTED]
cc2 [REDACTED]
[REDACTED]
[REDACTED]
[REDACTED]
[REDACTED]

- Stool collection (biomarker) at Baseline/Day 1 and Week 12 (if available)
- Standard 12-lead ECG at Baseline/Day 1
- Liver stiffness measurement by FibroScan at Week 12
- At the posttreatment follow-up visit, subjects will have a symptom-driven PE including assessments for ascites, HE, calculation of CP and MELD score, IBD symptom severity assessment and review for active IBD, for subjects with history of IBD (as appropriate, see Section 6.8.6), vital signs, weight, laboratory assessments including blood collection for biomarker assessments, urine pregnancy tests (for females of childbearing potential), **CCI** [REDACTED] and review of AEs and CMs.

Test Product, Dose, and Mode of Administration: CILO 30 mg (1 × 30 mg tablet), CILO 60 mg (2 × 30 mg tablets), or CILO 100 mg (1 × 100 mg tablet) administered orally once daily.

Reference Therapy, Dose, and Mode of Administration: None

Criteria for Evaluation:

Safety: Safety will be assessed during the study through the reporting of AEs, and by clinical laboratory tests and vital sign assessments at various time points during the study. Concomitant medication usage will also be assessed throughout the study.

CCI [REDACTED]

CCI [REDACTED]

Statistical Methods: Efficacy Analysis:

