In this study, we will further evaluate the frequency of pruritus in a population of subjects with PSC and cirrhosis taking CILO. The study is designed to dose escalate every 4 weeks based on investigator assessment of tolerability of CILO (particularly with respect to pruritus), with additional quantitative measures of pruritus (eg, the 5D-Itch and visual analog scale [VAS] questionnaires) performed every 4 weeks. For subjects who develop significant pruritus, a formal pruritus management plan has been included in this study which includes, temporary study drug dose interruption of CILO dosing, dose reduction, and supportive management with antihistamines and bile acid sequestrants.

Another potential risk of CILO treatment is drug-related hepatotoxicity. In nonclinical studies, effects on the liver have been limited to nonadverse mild increases in ALP and liver weights and minimal hepatocellular hypertrophy that are likely a pharmacological response to FXR agonism. There were no elevations in liver transaminases or changes in liver pathology (degeneration/necrosis) to suggest direct cellular damage. During the randomized phases of the Phase 2 NASH (GS-US-402-1852) and PSC studies (GS-US-428-4025), similar rates of treatment-emergent elevations in liver biochemistry tests were observed in CILO versus placebo-treated subjects. Specifically, Grade 3 or 4 ALT elevation was observed in 3.9% of subjects (6 of 154) treated with CILO and 2.6% of subjects (1 of 38) treated with placebo in these studies. Grade 3 or 4 AST elevations occurred in 4.5% (7 of 154) and 5.3% (2 of 38) of subjects, respectively. In the majority of these cases, an alternative etiology was identified including natural fluctuations in underlying disease activity and biliary obstruction in a subject with PSC that resolved following endoscopic intervention. To mitigate the potential risk of liver injury in this study, subjects will be monitored closely and defined rules for close observation and drug cessation due to elevated liver tests have been specified in the protocol (see Section 7.5. Toxicity Management: Observation for Drug-Induced Liver Injury).

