3. STUDY DESIGN

3.1. Study Design

[figure not shown]
This is a proof of concept, open-label study evaluating the safety and tolerability of CILO in subjects with PSC and compensated cirrhosis.

Eligible subjects will be enrolled and receive treatment with escalating doses of CILO over 12 weeks. Subjects will dose escalate at Week 4 (from 30 mg to 60 mg once daily) and Week 8 (from 60 mg to 100 mg once daily) if in the opinion of the principal investigator (PI) study drug is being tolerated.

Individual subject participation in the study can last up to 20 weeks, which includes a 4-week screening period, a 12-week treatment period (divided into three 4-week dosing stages at 30 mg QD, 60 mg QD, and 100 mg QD), and a follow-up visit 4 weeks after the Week 12 visit.

Study drug dosing may be interrupted for up to 4 consecutive weeks at the discretion of the PI if a subject experiences an AE (eg, intolerable pruritus) thought to be related to the study drug. During the period of study drug dose interruption, subjects are not required to attend in-clinic visits per the Study Procedures Table ([Appendix 2](#)) but will be monitored via weekly telephone follow-up visits (refer to Section [7.5.5](#)). If a study drug dose interruption requires reinitiation of a dosing stage, participation in the study could be extended from up to 20 weeks to up to 28 weeks to complete 4 consecutive weeks of dosing at each dose stage.

The overall study design is shown in the figure below:

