7.5.4. Pruritus Management

The development or worsening of pruritus during the study is a consideration for patients with PSC. Management of pruritus may include nonpharmacologic interventions (eg, skin moisturization, minimized heat exposure, avoidance of skin irritants, scratch reduction), topical corticosteroids, oral antihistamines, and/or bile acid sequestrants (eg, cholestyramine). Bile acid sequestrants must be taken more than 4 hours before or after the study drug dosing, as described in [Table 5-1](#). Rifampin may not be used for management of pruritus.

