7.5.5. Management of Study Drug Dose Interruption Due to AE

If subject experiences an AE (eg, intolerable pruritus) which in the opinion of the investigator may be related to the study drug, the subject may temporarily hold study drug at the investigator's discretion. If study drug dosing is held for longer than 5 days, this is considered a PI approved study drug dose interruption which may not last longer than 4 consecutive weeks. During this period, subjects are not required to attend in-clinic visits per Study Procedures Table ([Appendix 2](#)); however, will be monitored via weekly telephone follow-up visits. Female subjects of childbearing potential will be required to perform at home pregnancy tests every 2 weeks during a PI approved study drug dose interruption.

Following the PI approved study drug dose interruption (ie, the AE has resolved or in the case of pruritus, has returned to baseline severity), the subject may initiate a 4-week re-challenge of the most recent dose. In-clinic visits and associated assessments per [Appendix 2](#) will also resume, beginning with a repeat of the initial visit for that dose stage (ie, Day 1 for 30 mg, Week 4 for 60 mg, and Week 8 for 100 mg). If resumption of study drug is tolerated in the opinion of the investigator for 4 consecutive weeks, the study drug dose can be escalated (ie, subject must complete 4 consecutive weeks at 30 mg and 60 mg before escalating to 60 mg and 100 mg, respectively).

If after resumption of study drug the subject experiences another AE thought to be related to study drug (eg pruritus) that necessitates study drug interruption, the study drug should be stopped, and the medical monitor should be notified. Only a single study drug dose interruption period of up to 4 consecutive weeks is permitted.

For study drug dose interruptions due to AEs that are deemed unrelated to study drug in the opinion of the PI, the aforementioned approach should also be followed (ie, only 5-day drug interruption permitted before requirement to repeat 4 week dosing stage).

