2.3. Changes from Protocol-Specified Analysis

Due to limited subject enrollment in the study, part of safety summaries and listings (body weight, vital signs, prior and concomitant medications, electrocardiogram [ECG], and pharmacodynamic parameters) planned in the protocol will not be provided.

PSC Patient-Reported Outcome (PRO) is a novel endpoint. CCI [REDACTED]

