3.5.2. Outliers

Outliers of non-PK data will be identified during the data management and data analysis process, but no sensitivity analyses will be conducted. All data will be included in the data analysis.

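### SAP 7.4 drops all reporting of on-treatment concomitant medication, so the study report cannot show whether a subject escalated or completed only with treatment for itch

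*SAP*

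**What the plan says.** **Protocol.** Section 1.5 identifies pruritus as the primary risk of cilofexor and describes a management plan that includes "supportive management with antihistamines and bile acid sequestrants". Section 7.5.4 allows non-drug measures and "topical corticosteroids, oral antihistamines, and/or bile acid sequestrants (eg, cholestyramine"). Escalation at Weeks 4 and 8 takes place "if in the opinion of the principal investigator (PI) study drug is being tolerated" (3.1). After an interruption, the subject may be re-challenged once "the AE has resolved or in the case of pruritus, has returned to baseline severity" (7.5.5). Neither rule mentions whether antipruritic treatment is in use. The Synopsis, under the safety criteria for evaluation, adds: "Concomitant medication usage will also be assessed throughout the study". Section 5.4 requires concomitant medications to be recorded in source documents and on the eCRF through the follow-up visit.

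**SAP.** Section 7.4 reads: "Prior and concomitant medications will not be summarized or listed". Section 2.3 declares this as a change from the protocol. Because of limited enrollment, it drops "part of safety summaries and listings (body weight, vital signs, prior and concomitant medications", and ECG and pharmacodynamic parameters after them. The one item still taken from the medication page is UDCA use, yes or no, as a baseline characteristic (5.2).

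**The concern.** The study is open-label and has no control arm, and its primary endpoint is safety and tolerability (Protocol 8.1.2). The likeliest tolerability problem is one for which the protocol allows add-on treatment while dosing continues. Two subjects can therefore both reach 100 mg, one unaided and one on an antihistamine or a sequestrant. They carry different information about how well the drug is tolerated. If the treatment works, it lowers recorded itch and may avert an interruption. Without any record of it in the outputs, the reader sees only the favorable course.

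A reader of the study report would want to know how many subjects needed such treatment, at which dose stage, and whether they then escalated. Under SAP 7.4 as written, no readable output answers any of these.

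**Working it through.** The plan gives no figure to reproduce: Protocol 8.9 and SAP 1.3 state that no power calculation was made. The check is whether the planned outputs can carry the information, followed by a rough indication of size.

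**1. Two hypothetical subjects traced through the readable outputs.** Both have Grade 2 pruritus in the 30 mg stage and both escalate to 100 mg. Subject A takes nothing for it; subject B takes an antihistamine throughout.

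| Planned output | Source | A and B distinguishable? |
|---|---|---|
| TEAEs by SOC/PT, maximum severity, Grade 2 or higher | SAP 7.1.6 | No, if graded alike |
| TEAEs leading to interruption or discontinuation | SAP 7.1.6 | No, neither stopped |
| Disposition, with interruptions by dose level | SAP 4.1 | No |
| Exposure, adherence, accountability listing | SAP 4.2 | No |
| UDCA use at baseline | SAP 5.2 | No, not an itch treatment |
| Concomitant medication table or listing | SAP 7.4 | Would distinguish them, but is dropped |

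The SAP does not say that the adverse event listing will carry treatment given for the event.

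**2. Does the stated reason cover a listing?** Limited enrollment is a fair reason to omit a summary table. Yet for the same subjects the SAP keeps by-subject listings of adverse events (7.1.6), laboratory results (7.2), drug administration and accountability (4.2.2.1), medical history (5.3) and IBD symptoms (7.6). Few subjects favor listings over tables, so the reason does not reach the listing.

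**3. Are the data there?** Medications are recorded on the eCRF (Protocol 5.4). Source data include start and end dates and, if relevant, dose and dose changes (Protocol 9.1.6). Dose stage follows from comparing the start date with the dosing dates. Neither section mentions the indication for each medication.

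**4. Illustrative size.** Inputs from Protocol 1.5, the earlier noncirrhotic PSC study over 12 weeks:
- any-grade pruritus on cilofexor: 13/42 = 0.310
- Grade 2-3: (3 + 4)/(22 + 20) = 7/42 = 0.167

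The planned number is about 20 (Protocol 4.1). SAP 1 says enrollment was stopped early and gives no final number, so N is assumed to lie between 5 and 20. The expected number is N × p, and the chance of at least one case is 1 − (1 − p)^N.

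| Assumed N | Any grade: expected; P(≥1) | Grade 2-3: expected; P(≥1) | One subject as share of N |
|---|---|---|---|
| 5 | 1.5; 0.843 | 0.8; 0.598 | 20% |
| 10 | 3.1; 0.975 | 1.7; 0.838 | 10% |
| 20 | 6.2; 0.999 | 3.3; 0.974 | 5% |

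For N = 10: 10 × 13/42 = 3.1 and 1 − (29/42)^10 = 0.975; 10 × 7/42 = 1.7 and 1 − (35/42)^10 = 0.838.

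These are counts of subjects with pruritus, not of subjects treated for it. The documents give no rate of antipruritic use.

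**The case against.** The best defense is that this is a declared reporting choice, with a reason, in an exploratory study without formal testing. The data are still collected. Protocol 8.1.2 builds the primary endpoint from TEAEs, laboratory tests and vital signs and does not name medication use there. Pruritus recorded as an adverse event stays visible by preferred term, grade, and effect on dosing. All of this stands, and it limits the point to missing context. It does not explain why a listing is dropped when comparable listings are kept, or why an item named among the Synopsis safety criteria leaves no on-treatment trace.

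Stronger readings are tempting, and the documents do not support them:

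- *The SAP reports no medication at all.* It reports baseline UDCA use. What is missing is on-treatment use, including any antipruritic agent.
- *Subjects will be misclassified as tolerating the drug.* No readable output classes anyone as tolerant or not, so there is no variable to bias.
- *The SAP knowingly pools records affected by itch treatment.* The sentence "All data will be included in the data analysis" in SAP 3.5.2 is the rule for outliers and says nothing about co-treatment. SAP Section 6 and the text after 7.6 are largely blacked out, so whether itch or biomarker records are flagged there cannot be judged.
- *A definite number of the 20 planned subjects will be affected.* Enrollment stopped early, moderate to severe itch is an exclusion (Protocol 4.3), the rates come from noncirrhotic subjects, and no share treated is given. Subjects whose itch led to interruption or discontinuation would in any case be reported.

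**Conclusion.** The point holds as a reporting gap. It is not a data gap, and it is not a hidden conflict between the documents. Protocol and SAP together allow a subject to continue and escalate on antipruritic treatment, while SAP 7.4, without exception, removes the only readable output that would show it. The report could describe how much pruritus occurred but not whether completion or escalation depended on treating it.

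The size is illustrative. If the earlier noncirrhotic rates carry over and 10 subjects were treated, about 3.1 would have pruritus of any grade and 1.7 of Grade 2-3. At least one case of any grade is likely across the assumed range of N (0.843 at N = 5), and at the smaller sizes one subject is 10% to 20% of the sample. How many would receive treatment is unknown. The gap should be closed because it bears on the primary tolerability conclusion and is cheap to close; it does not invalidate the adverse event analysis.

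**What to change.** Replace SAP 7.4 with:

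1. A by-subject listing of concomitant medications with start and stop dates and the dose stage at start. Flag antihistamines, topical corticosteroids, bile acid sequestrants and changes in UDCA. Flag the antipruritic classes by indication if the eCRF collects it, otherwise by class.
2. The number of subjects who started or increased an antipruritic agent after Day 1, by dose stage.

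Remove concomitant medications from the list of dropped outputs in SAP 2.3.

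Where itch or biomarker data are reported, mark the records taken after such treatment began. Do not repeat the summaries with those records excluded. That would condition on a post-baseline event and tend to remove the subjects most affected by itch, which could make the drug look better tolerated. Marking applies only to outputs actually produced, since SAP 2.3 also drops pharmacodynamic parameters.

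The cost is SAP wording, one listing and one count from data already recorded. The downside is small: if indication is not collected, class-based flags will include some use for other reasons, which a footnote should say. No dose, escalation or treatment rule changes.

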7.5. Electrocardiogram Results

Electrocardiogram data will not be summarized or listed.

7.6. Other Safety Measures

A by-subject listing sorted by subject ID number will be provided for subjects who become pregnant during the study.

IBD Symptom Severity Assessment is a survey for the assessment of IBD that considers stool frequency, rectal bleeding, and physician assessment of IBD for disease severity assessment. A by-subject listing of IBD Symptom Severity Assessment will be provided by subject ID number and visit in chronological order for subjects with history of IBD.

CC

CCI

CCI

CCI

cc

[REDACTED]

11. SOFTWARE

SAS® Software Version 9.4. SAS Institute Inc., Cary, NC, USA.

Phoenix WinNonlin® 8.2. Pharsight Corporation, Princeton, NJ, USA.

12. SAP REVISION

Revision Date (DD MMM YYYY)	Section	Summary of Revision	Reason for Revision

Appendix 1. Study Procedures Table

Study Procedures Table – Screening to Follow-Up Visit

Assessments	Screening ^a	Treatment Visits (± 3 days) ^{b c d}						Follow-Up (± 5 days)
		Baseline/ Day 1	Week 1	Week 4	Week 8	Week 12	ET ^e	
Subject Fasting		X	X	X	X	X	X	X
Written Informed Consent	X							
Medical History	X							
Review Inclusion/Exclusion Criteria	X	X						
Physical Examination ^f	X	X	X	X	X	X	X	X
Assess ascites and HE	X	X	X	X	X	X	X	X
CP and MELD Scores	X	X	X	X	X	X	X	X
Vital Signs ^g and Body Weight	X	X	X	X	X	X	X	X
Height	X							
IBD Symptom Severity Assessment ^h	X	X		X	X	X	X	X
CCI								
Review for Active IBD ⁱ		X	X	X	X	X	X	X
12-lead ECG	X	X						
CCI								
Concomitant Medications	X	X	X	X	X	X	X	X
Adverse Events	X	X	X	X	X	X	X	X
Dispense Study Drug		X		X	X			

Assessments	Screening ^a	Treatment Visits (± 3 days) ^{b c d}						Follow-Up (± 5 days)
		Baseline/ Day 1	Week 1	Week 4	Week 8	Week 12	ET ^e	
Review Study Drug Compliance			X	X	X	X	X	
Laboratory Assessments								
Chemistry, eGFR, Hematology, Coagulation Panel	X	X	X	X	X	X	X	X
Lipid Profile		X		X	X	X	X	X
C-Peptide, Insulin and HbA _{1c}		X					X	X
HIV-1, HBV and HCV Serology	X							
Urine Drug Screen	X							
Pregnancy Testing ¹	X	X		X	X	X	X	X
Serum FSH ^m	X							
Stool Collection (if available)		X					X	
Blood for Biomarkers	X	X	X	X	X	X	X	X

CCI
 CCI

AE = adverse event; CLDQ = Chronic Liver Disease Questionnaire; CP = Child-Pugh; ECG = electrocardiogram; EDC = electronic data capture; eGFR = estimated glomerular filtration rate; EQ-5D = EuroQol five dimensions; ET = early termination; FSH = follicle-stimulating hormone; HBV = hepatitis B virus; HbA_{1c} = hemoglobin A_{1c}; HCV = hepatitis C virus; HE = hepatic encephalopathy; HIV-1 = human immunodeficiency virus type 1; IBD = inflammatory bowel disease; IWRs = interactive web response system; MELD = model for end-stage liver disease; PD = pharmacodynamic(s); PE = physical examination; PI = principal investigator; PK = pharmacokinetic(s);

PRO = patient-reported outcome; PSC = primary sclerosing cholangitis; QoL = quality of life; SIBDQ = short inflammatory bowel disease questionnaire; VAS = visual analog scale

- a Subjects will be screened up to 4 weeks prior to treatment. The screening period may be extended under special circumstances with the explicit approval of the medical monitor.
- b At the discretion of the PI, study drug dosing may be temporarily interrupted if subject experiences an AE thought to be related to study drug, including pruritus. In the event this occurs, the PI should notify the medical monitor and the subject should hold study drug until the AE has resolved or pruritus has returned to baseline levels. When resuming study drug, the subject should resume dosing at the prior dose and restart a 4-week challenge on this dose. If subject tolerates study drug for the subsequent 4 weeks, the subject may dose escalate at the discretion of the PI (refer to Section 7.5.5 of the protocol). The same in-clinic visits and associated study assessments during regular visits would be performed when re-challenging a dose (referenced as postinterruption visit in IWRS and EDC). If reinitiating dose stage of 30 mg study drug, subjects are not required to redo Baseline/Day1 QoLs.
- c Telephone follow-up visit will occur only for subjects on PI approved study drug dose interruption. During the period of study drug dose interruption, subjects will be contacted on a weekly basis for up to 4 consecutive weeks (refer to Section 6.4.2 of the protocol).
- d Treatment visits windows are ± 3 days unless otherwise stated (see Section 6.4 of the protocol).
- e Subjects prematurely discontinuing from the study should complete an ET visit within 30 days of last study visit.
- f Symptom-directed PE. The focus of a symptom-driven physical examination will be determined by the investigator based on subject complaint. A complete PE will be completed at screening.
- g Vital signs include heart rate, systolic and diastolic blood pressure, respiratory rate, and body temperature.
- h For subjects with history of IBD. Assessment of Bleeding History and Daily Bowel Movement Count as detailed in Appendix 6 of the protocol.

i For subjects with history of IBD, any evidence of active IBD seen on routinely performed colonoscopy will be captured.

l Females of childbearing potential only (see Appendix 4 of the protocol). Serum pregnancy tests at screening and urine pregnancy tests at Day 1, Weeks 4, 8, 12 while on treatment. Urine pregnancy test to be taken at home every 2 weeks during PI approved study drug dose interruption.

m Women of any age with amenorrhea of ≥ 12 months (see Appendix 4 of the protocol).

